6.6 Supportive Care

Patients will receive full supportive care while on this study. This includes blood product support, antibiotic treatment and treatment of other newly diagnosed or concurrent medical conditions. All blood products and concomitant medications such as anti-diarrheal, analgesics, anti-emetics received from the first administration of study drugs until 30 days after the final dose are to be recorded in the medical record.

All patients may receive prophylaxis with either an H-2 blocker or proton pump inhibitor while on study medications if needed or if dexamethasone is added. Suggested medications included ranitidine 150 mg oral twice daily or omeprazole 20 mg oral daily or equivalent.

Patients may receive bisphosphonates at physician's discretion.

Patients may receive local radiation for pain control.

6.6.1 Thromboprophylaxis

Lenalidomide increases the risk of thrombotic events in patients who are at high risk or with a history of thrombosis, in particular when combined with other drugs known to cause thrombosis. When lenalidomide is combined with other agents such as steroids (e.g. dexamethasone, prednisone), anthracyclines (doxil, adriamycin) and erythropoietin, the risk of thrombosis is increased.

It is required that patients receive 81-325 mg of aspirin (enteric-coated is preferred) as thromboprophylaxis, equivalent or more intensive anticoagulation strategies with low molecular weight heparins or full-dose warfarin are permitted.

6.6.2 Growth factors

Prophylactic use of growth factors is not recommended.

6.7 Requirements at the beginning of each cycle

A new course of treatment may begin on the scheduled Day 1 of a new cycle if:

- The ANC is $\geq 1,000/\mu\text{L}$;
- The platelet count is $\geq 50,000/\mu\text{L}$;
- Any lenalidomide-related allergic reaction/hypersensitivity or sinus bradycardia/ other cardiac arrhythmia adverse event that may have occurred has resolved to \leq grade 1 severity;
- Any other lenalidomide-related adverse event that may have occurred has resolved to \leq grade 2 severity.

If these conditions are not met on Day 1 of a new cycle, the subject will be evaluated weekly and a new cycle of therapy will not be initiated until the toxicity has resolved as described above. Patients unable to initiate a new cycle of therapy within 4 weeks due to treatment related toxicity will be removed from study.

- If lenalidomide dosing was held during the previous cycle and was restarted with a one-level dose reduction without requiring an interruption for the remainder of the cycle, then that reduced dose level will be initiated on Day 1 of the new cycle.
- If lenalidomide dosing was omitted for the remainder of the previous cycle or if the new cycle is delayed due to lenalidomide related toxicity newly encountered on the scheduled Day 1, then the new cycle will be started with a one-level dose reduction of lenalidomide.

6.8 Patient Withdrawal

A patient should be removed from the study whenever it is necessary to safeguard his/her welfare. Occurrence of a significant adverse event or laboratory abnormalities unexpected for these patients may also necessitate discontinuation from the study. Additional reasons for removing a patient from the study are:

- Patients who participate in another investigational drug trial.
- The occurrence of unacceptable toxicity indicating the need for cessation of treatment. Patients may continue with correlative studies.
- Patient has progressive disease while receiving treatment.
- The physician feels it is in the best interest of the patient to stop treatment and the physician may determine whether to continue with correlative studies.
- Patients who express a desire to withdraw from the study (the patient has the right to withdraw for any reason without prejudice).
- Non-compliance by the patient with protocol requirements.
- Patient is lost to follow-up. If a patient does not return for scheduled visits, every effort should be made to re-establish contact. In any circumstance, every effort should be made to document patient outcome, if possible.
- Patient becomes pregnant.
- Any other reasons deemed by the principal investigator and treating physician.
- Termination of the study.

The reason for any patient withdrawal from the study should be recorded on the case report form (CRF) and the occurrence should be reported to the OSU principal investigator by email. These patients who withdraw from the study in the phase II portion of the trial will not be replaced. When a patient is removed from the study, he/she will receive treatment according to the standard of care (SOC) in the medical center and will be followed-up according to the study schedule whenever possible.

The investigator should complete all end of treatment procedures when a patient withdraws from treatment. A patient who is removed from the study by the investigator due to an adverse event (AE) or serious adverse event (SAE) will be followed until resolution of the toxicity to Grade 1 or baseline. All the tests that are required to assess the patient condition will be made as frequent as necessary until the AE or SAE has been resolved. Samples that have already been obtained will be processed.

A patient who withdraws consent before starting the study will not be followed.

A patient who is removed from the study by the investigator since he/she did not keep the appointments will be hard to follow given the circumstances. The extreme situation of this occurrence is a patient who is defined as "lost to follow-up". Attempts to follow up on the subject will be made as long as the consent has not been withdrawn by the subject. Samples that have already been obtained will be processed.

A patient who initiated another treatment not allowed in the protocol is to be removed from the study by the investigator. Follow up will be only for safety per above. Attempts to continue the follow up of the patient by monthly phone calls or other means will be made to collect information on the patient's survival. Samples that have already been obtained will be processed.

For patients who withdraw consent, there must be clear documentation of whether the subject withdraws consents to treatment only (i.e. agrees to follow-up) or withdraws consent to treatment and follow-up.

6.9 Schedule of Tests and Observations

6.9.1 Screening

All screening tests must be performed within 4 weeks prior to starting protocol-based therapy with the exception of obtaining informed consent, which should be conducted within the timeframe outlined in local policy (if applicable).

6.9.2 Evaluation during treatment

Clinical examination, ECOG/WHO PS, vital signs, toxicity assessment and documentation of concomitant medications will be performed at each outpatient visit. Toxicity will be assessed according to the NCI CTCAE

6.9.3 Post-treatment Follow-up

After the end of study treatment (whatever the reason for discontinuation), the patient will be followed for at least 30 days, during which time all procedures for the reporting of SAEs will be followed. All patients who discontinue the trial secondary to an adverse event thought to be related to protocol therapy (probably, possible, or definite) should be followed until resolution, stabilization, return to a baseline condition, or death. Overall and progression free survival will be determined through clinic visits or phone interviews with clinical research staff.

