5.2 Definition of Dose Limiting Toxicity

Patients will be monitored for safety by assessing toxicities as graded by the NCI CTCAE v4.0. Dose limiting toxicity (DLT) will be defined as one or more of the following toxicities considered to be at least possibly related to one of the study drugs during Cycle 1

- Grade 3 or greater nonhematologic toxicity with the exception of Grade 3 nausea, vomiting and diarrhea that responds to supportive therapy.
- Grade 4 thrombocytopenia, or grade 3 thrombocytopenia with bleeding, or any requirement for platelets transfusion
- Grade 4 neutropenia persisting for more than 5 days.
- Grade 3 or greater febrile neutropenia (temperature $\geq 38.5^{\circ}\text{C}$)
- Grade 4 anemia, unexplained by underlying disease

Patients that experience a lenalidomide-related hematologic DLT may continue on therapy if the event resolves, the investigator considers it in the best interest of the patient to continue and the patient qualifies for initiation of the next cycle with standard of care lenalidomide dose reduction.

Discontinuation of treatment due to disease progression will not constitute a DLT.

After 4 cycles of therapy or earlier if clinically indicated, response determination will be assessed by the IMWG criteria. At the end of Cycle 4, if a subject has responded (complete or partial response) or has stable disease, dosing with Nivolumab and lenalidomide will continue for a minimum of 8 additional cycles or until withdrawal.

If disease progression is observed at the end of Cycle 4 evaluation, all study therapy will be discontinued. Confirmation of progression of disease will be done according to the IMWG criteria.

Following the 30-day post-treatment follow-up assessment, additional evaluations will occur once per month (unless subject discontinued due to progression) until the earliest of the following events: disease progression, the time of initiation of new therapy, death or study completion.

Study completion is defined as 30 days after the last subject remaining on study medication discontinues study medication.

An independent Data Monitoring Committee will continue oversight of this trial.

Treatment will continue until Progression of disease, death, unacceptable toxicity or patient or treating physician decision to discontinue therapy.

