5.3 Duration of Treatment

Patient can continue study treatment at the treating physician's discretion. Patients achieving at least a stable disease can continue treatment until one of the following is reached:

- Progression of disease
- Death
- Unacceptable toxicity

- Patient decision
- Treatment delay greater than 4 weeks.

Overall response will be assessed after 4, 8, and 12 cycles. If disease progression is observed at the end of Cycle 4 evaluation, all study therapy will be discontinued. In addition, study therapy will be discontinued at the time of disease progression as noted above.

For subjects who withdraw consent, there must be clear documentation of whether the subject withdraws consents to treatment only (i.e. agrees to follow-up) or withdraws consent to treatment and follow-up.

Following the 30-day post-treatment follow-up assessment, additional evaluations will occur once per month (unless subject discontinued due to progression) until the earliest of the following events:

- Disease progression,
- The time of initiation of new therapy,
- Death.

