- h. Baseline and periodic ECGs should be performed during treatment as indicated in the flow chart. In patients who have ECG abnormalities, ECGs should be performed more routinely as clinically indicated. ECGs post-baseline should be performed as indicated
- i. Myeloma monoclonal protein assessments (Serum protein electrophoresis & immunofixation, immunoglobulin levels, serum free light chain assay) will be performed on day 1 of each cycle as well as off study.
- j. 24hr urine monoclonal protein assessment (Urine protein electrophoresis & immunofixation) will be performed at screening and as required for response assessment.
- k. Unilateral bone marrow (BM) biopsy will be done at baseline and at end of 4th cycle and evidence of progression for patients with non-secretory multiple myeloma
- l. Lenalidomide must be prescribed through and in compliance with Celgene's RevAssist® program. Prescriptions must be filled within 7 days. Any unused lenalidomide should be returned to the patient for disposition in accordance with the RevAssist® program.
- m. Dexamethasone will be started on cycle 3 only if stable disease after 2 cycles.
- n. Lenalidomide and dexamethasone will start on day 1 of each cycle. Patients will do not need to be in clinic to initiate this as all patients would have been exposed to both. Lenalidomide will be ordered for the next cycle. A pregnancy test (urine or B-HCG) will also be ordered at this time and must be negative prior to starting treatment.
- o. Laboratory correlative studies will be obtained. This will be collected through C5D1, at the off study visit, and at 1, 3, and 6 months post off-study. Off-study correlates should be obtained at the time the patient is removed from protocol for any reason.
- p. Vital signs (temperature, blood pressure, pulse rate, respiratory rate) and ECG will be closely monitored prior to, during, and after first drug infusion to avoid general infusion-related reactions. Routine vital signs with subsequent infusions, unless indicated otherwise.
- q. Correlative studies for the bone marrow aspirate will be done at screening, cycle 5 day 1, and at the off study visit.

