7.3 Clinical outcome definitions

Time to progression: TTP will be defined as the time from start of treatment until the date he or she has progression or dies. Any subject who has received study treatment but has neither progressed nor died will be censored on the date of his or her last tumor assessment. A subject who has not received study treatment and who has neither progressed nor died will be censored on the day he or she was enrolled.

Progression Free Survival: PFS will be defined as the time from study entry until disease progression or death at trial closure for the per protocol population. Patients who withdraw from the trial prior to disease progression and who are either lost to follow-up, die or who begin alternative treatments prior to progression, will have their data censored as of the date considered to be lost to follow-up, date of death, or the first day of alternative therapy.

Time to Response: A subject's time to response is defined as the time from first dose of study therapy until measurement criteria are first met for [VG]PR or CR or SD (whichever status is recorded first). Time to response is computed only for subjects whose best response is [VG] PR or CR.

Duration of Overall Response: The duration of overall response will be computed for subjects whose best response is either [VG] PR or CR or SD. It will be measured from the time measurement criteria are first met for complete response or partial response (whichever status is recorded first) until the first date of progressive disease or death. Subjects who neither progress nor die will be censored on the date of their last tumor assessment.

Overall Survival: A subject's survival time will be defined as the time from start of treatment to the date of his or her death. If the subject has not died, survival will be censored on last date the subject was known to be alive.

Response Rate: The tumor response rate will be defined as the total number of subjects whose best response is PR or VGPR or CR or SD, divided by the number of per protocol patients.

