		70	Cares for self, unable to carry on normal activity or to do active work.
2	In bed <50% of the time. Ambulatory and capable of all self-care, but unable to carry out any work activities. Up and about more than 50% of waking hours.	60	Requires occasional assistance, but is able to care for most of his/her needs.
		50	Requires considerable assistance and frequent medical care.
3	In bed >50% of the time. Capable of only limited self-care, confined to bed or chair more than 50% of waking hours.	40	Disabled, requires special care and assistance.
		30	Severely disabled, hospitalization indicated. Death not imminent.
4	100% bedridden. Completely disabled. Cannot carry on any self-care. Totally confined to bed or chair.	20	Very sick, hospitalization indicated. Death not imminent.
		10	Moribund, fatal processes progressing rapidly.
5	Dead.	0	Dead.

13 Appendix. IMWG Response Criteria

Serum and urine M-protein estimates will be performed every 4 weeks; except for assessment of CR, patients with measurable disease restricted to the SPEP (or UPEP) will need to be followed only by SPEP (or UPEP). Responses will be assessed according to the criteria of the International Myeloma Working Group⁴⁶, and characterized as follows:

Response Category	Response Criteria ^a
SCR	CR as defined below plus 
 • Normal FLC ration and • Absence of clonal cells in bone marrow^b by immunohistochemistry or immunofluorescence^c
CR	Negative immunofixation on the serum and urine and disappearance of any soft tissue plasmacytomas and $\leq 5\%$ plasma cells in bone marrow ^b
VGPR	Serum and urine M-protein detectable by immunofixation but not on electrophoresis or 90% or greater reduction in serum M-protein plus urine M-protein level < 100 mg per 24 hours

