Relapse from CR ⁱ	Any one or more of the following: 
 • Reappearance of serum or urine M-protein by immunofixation or electrophoresis • Development of $\ge 5\%$ plasma cells in the bone marrow^j • Appearance of any other sign or progression

a. All response categories require two consecutive assessments made at anytime before the institution of any new therapy; all categories also require no known evidence of progressive or new bone lesions if radiographic studies were performed. Radiographic studies are not required to satisfy these response criteria.

b. Confirmation with repeat biopsy not necessary.

c. Presence/absence of clonal cells is based upon the κ/λ ratio by immunohistochemistry and/or immunofluorescence requires a minimum of 100 plasma cells for analysis. An abnormal ration reflecting presence of an abnormal clone is κ/λ of $> 4:1$ or $< 1:2$.

d. Applicable only to patients who have 'measurable' disease defined by at least one of the following three measurements: Serum M-protein $\ge 1 \text{ g/dl}$, Urine M-protein $\ge 200 \text{ mg/24hour}$, Serum FLC assay involved FLC level $\ge 10 \text{ mg/dl}$ provided serum FLC ration is abnormal.

e. Not recommended for use as an indicator of response; stability of disease is best described by providing the time to progression estimates).

f. All relapse categories require two consecutive assessments made at anytime before classification as relapse or disease progression and/or the institution of any new therapy.

g. For progressive disease, serum M-component increases of $\ge 1 \text{ gm/dl}$ are sufficient to define relapse if starting M-component is $\ge 5 \text{ g/dl}$.

h. Relapse from CR has the 5% cutoff versus 10% for other categories or relapse.

i. To only be used if the end point studied is disease free survival. For purposes of calculating time to progression and progression-free survival, CR patients should also be evaluated using criteria listed above for progressive disease.

j. Relapse from CR has the 5% cutoff versus 10% for other categories of relapse.

14 Appendix. NYHA Cardiac Disease

Class	Functional Capacity	Objective Assessment
I	Patients with cardiac disease but without resulting limitations of physical activity. Ordinary physical activity does not cause undue fatigue, palpitation, dyspnea, or anginal pain.	No objective evidence of cardiovascular disease.

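### PFS is censored at the date a patient is considered lost, and no disease test is specified after the off-study visit, so unassessed time can count as progression-free

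*Combined protocol and SAP*

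**What the plan says.** **Ascertainment after treatment.** Section 6.9.3 says that after treatment ends "the patient will be followed for at least 30 days", and then: "Overall and progression free survival will be determined through clinic visits or phone interviews with clinical research staff". Sections 5.2 and 5.3 add that, for patients who stopped without progression, "additional evaluations will occur once per month (unless subject discontinued due to progression) until the earliest of the following events" occurs. Progression, new therapy and death are on both lists of end events. Neither section says what an evaluation contains.

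**Disease tests.** Appendix 13 says "Serum and urine M-protein estimates will be performed every 4 weeks" but does not say whether this continues off treatment. The calendar notes in section 6.9.6 say the myeloma protein tests "will be performed on day 1 of each cycle as well as off study". After the off-study visit the calendar lists only correlative samples, at 1, 3 and 6 months.

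**Standard for progression.** Appendix 13, footnote f: "All relapse categories require two consecutive assessments made at anytime before classification as relapse or disease progression". The listed criteria are M-protein, light chains, marrow plasma cells, bone lesions or plasmacytomas, and calcium.

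**Censoring.** Section 7.3 says that patients who withdraw before progression and are lost "will have their data censored as of the date considered to be lost to follow-up". Those who start another treatment are censored on its first day, and those who die are censored at death. TTP and duration of response are censored at the last tumor assessment.

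**Status.** PFS is a secondary endpoint (section 2.4). Section 7.1.1 describes its Kaplan-Meier analysis as exploratory and mainly descriptive.

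**The concern.** A phone call can establish that a patient is alive. It cannot itself supply a confirmed rise in M-protein or light chains. A patient who stops for toxicity or by choice has a disease assessment at the off-study visit. After that the plan requires monthly contact but names no disease test. If such a patient is later declared lost, the PFS rule keeps the patient in the risk set, as progression-free, up to that declaration. The time since the last assessment adds to the denominator but can contribute no observed progression, so the curve falls too slowly.

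Two details sharpen this. First, section 7.3 counts death as an event in TTP as well as in PFS. The two endpoints are therefore nearly the same, yet the same lost patient would be censored on different dates. Second, the PFS paragraph counts death as an event and then lists date of death among the censoring dates for withdrawn patients. That is contradictory, and censoring those deaths would also push PFS upward.

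At stake is the accuracy of a named secondary endpoint reported from 18 patients.

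**Working it through.** The documents give no PFS estimate, event count or loss rate, so there is no figure to reproduce. The check asks how far the stated rule could move the estimate.

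**1. Assumed inputs.** True PFS is exponential with median 6.0 months, so λ = ln 2 / 6 = 0.1155 per month. This lies between the 3.9 and 7.7 months that section 1.3.1 quotes for single-agent lenalidomide. Thirty percent of patients have a potential stopping time uniform over months 0 to 4, which takes effect only if it precedes progression. The share who stop without progression is

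0.30 × (1 − e^(−4λ)) / (4λ) = 0.30 × (1 − 0.6300) / 0.4621 = 0.24.

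They are declared lost L months after stopping, and no progression is detected after they stop.

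**2. Risk set under the planned rule.**

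- Still assessed and progression-free: A(t) = 2^(−t/6) × (1 − 0.30 × min(t/4, 1)).
- Stopped but not yet declared lost: B(t) = (0.30/4) × ∫ e^(−λs) ds, with s from max(0, t − L) to min(t, 4).

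Only A can produce events, so Kaplan-Meier sees hazard λA/(A + B). Its median m solves m − ∫₀^m B/(A + B) dt = 6. The excess over 6 months is therefore that integral.

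Example, L = 3 and t = 3: A = 0.7071 × 0.775 = 0.548; B = 0.075 × (1 − 0.7071)/0.1155 = 0.190; B/(A + B) = 0.258.

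**3. Results.** B/(A + B) is zero at month 0 and again from month 4 + L, so the trapezoid rule on monthly points is the plain sum.

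- L = 1, months 1 to 4: 0.079 + 0.086 + 0.093 + 0.102 = 0.36. Median 6.36.
- L = 3, months 1 to 6: 0.079 + 0.166 + 0.258 + 0.278 + 0.213 + 0.125 = 1.12. Median 7.12.
- Censoring at the last assessment gives B = 0, so the median is 6.0.
- If every later progression is detected, no patient is carried unassessed and the median is again 6.0.

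A simulation of the same setting gave about 6.3 to 7.1 months, which agrees closely.

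**4. Wider range.** A second simulation (400,000 patients per scenario) used exponential stopping times and no detection after stopping. Stopping share, gap and later hazard are all assumed. The first five columns describe the scenario; the last three give 6-month PFS.

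| True median without stopping (months) | Stop without progression | Gap to declared lost | Hazard after stopping | True | Planned rule | Last assessment |
|---|---|---|---|---|---|---|
| 7.7 | 10% | 1 month | same | 58.4% | 58.6% | 58.3% |
| 6 | 20% | 3 months | same | 50.0% | 52.6% | 50.1% |
| 6 | 30% | 3 months | doubled | 46.3% | 54.4% | 50.0% |
| 6 | 40% | 6 months | doubled | 44.4% | 58.9% | 50.0% |
| 3.9 | 40% | 6 months | doubled | 27.2% | 50.2% | 34.6% |

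The planned rule overstates 6-month PFS by 0.2 points (58.6 − 58.4) to 23 points (50.2 − 27.2). With half of later progressions detected, the second row falls from 52.6% to 51.3%. With all detected, the excess is zero in every row.

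Re-dating the censoring removes the bias when stopping is unrelated to prognosis. When the hazard doubles after stopping, part remains: 50.0 − 46.3 = 3.7 points in the third row and 50.0 − 44.4 = 5.6 points in the fourth.

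**The case against.** The strongest reply is that the plan already provides for follow-up. Monthly evaluations are required for every patient who stopped without progression, and progression is one of the events that ends them. Appendix 13 sets M-protein every 4 weeks. Section 6.8 follows removed patients on the study schedule where possible. The off-study visit includes serum and urine protein tests. Section 6.9.3 offers two routes for two endpoints and does not waive the IMWG standard. Where section 6.8 specifies phone calls after a non-protocol treatment, they are for survival.

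Much of this stands. A reader might infer that progression will be missed and median PFS will be too long. The documents do not support that certainty: if sites run M-protein tests at the monthly evaluations, the bias is about zero. The reply does not close the gap, because the evaluations have no stated content, the 4-weekly tests are not extended off treatment, and the study schedule lists no disease test after the off-study visit.

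A reader might also infer a shift of two months or more. A median of 8.1 months can be produced from a true 6.0, but only if every stopper's progression goes unseen and each is censored at new therapy 2 months after true progression. With 80% detection that falls to about 6.3. Neither is an expected effect.

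The consequence is also limited. With 18 fully observed patients and a true median of 6 months, simulated Kaplan-Meier medians span about 2.6 to 10.2 months (95%), far wider than the shift shown above.

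**Conclusion.** The point holds as a gap in the rules, not as a demonstrated error. The plan permits time after the last disease assessment to count as progression-free, and it uses a different censoring date for PFS than for TTP and response duration. Any resulting bias in Kaplan-Meier PFS is upward.

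Its size cannot be known from the documents. It is about zero if the monthly evaluations detect progression. It is roughly 0.4 to 1.1 months on a 6.0-month median if 24% stop without progression, are declared lost 1 to 3 months after their last assessment, and nothing is detected. The stopping share, gap and detection rate are all assumptions.

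The contradiction over death needs no assumption. One paragraph both counts death as an event and censors at it.

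It would be wrong to infer that the trial's conclusion is at risk. The rule for 18 patients in section 7.1.1 uses response only, and PFS is exploratory.

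**What to change.** **Section 7.3.** Censor PFS at the last adequate disease assessment before loss to follow-up or new therapy, matching TTP. Remove date of death from the PFS censoring list, so that death is an event throughout.

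**Section 6.9.3.** Limit phone contact to survival status and to obtaining outside results. At the monthly evaluations already planned in sections 5.2 and 5.3, record available local M-protein and free light chain results for patients off treatment without progression.

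**Cost.** A few sentences in two sections, minor data collection for the patients who stop without progression, and slightly shorter PFS follow-up for those censored. Re-dating alone does not remove bias if patients who stop have a worse prognosis and their later progression stays unobserved. Recording the monthly results addresses that part, as far as results are available.
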